2.5 Inferential Analyses

A comparison will be made between the cohorts with regard to safety and tolerability. For this aim a Fisher's exact test will be calculated to compare the following treatment groups in the summary table for adverse events:

- Cohort 1 PP-001 vs. Cohort 4 PP-001
- Cohort 2 PP-001 vs. Cohort 4 PP-001
- Cohort 3 PP-001 vs. Cohort 4 PP-001
- Cohort 1-3 PP-001 pooled vs. Placebo subjects from all Cohort 1-3
- Cohort 4 PP-001 vs. Placebo subjects from Cohort 4

NOTE: The study is not powered for p-values and the p-values are just calculated for exploratory reason.

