5.2 Timing of Dosing and Dose Administration

Cohorts 1-3:

Subjects will receive IP on Day 0 (single dose) and then Days 8–19 (48 doses).

On Day 0, the IP dose will be administered in house by site staff. Staff will administer a single drop of IP into one eye.

On Day 8 and 9, the IP doses will be administered in house by site staff. Staff will administer a single drop of IP into one eye four times throughout the dosing day separated by at least 4 hours.

On Days 10–19, the IP will be self-administered. Subjects will administer a single drop of IP into one eye four times throughout each dosing day separated by at least 4 hours.

Cohort 4:

Subjects will receive IP on Days 0-11 (24 doses).

On Day 0 and 1, the first instillation will be performed in house by site staff. Staff will administer a single drop of IP into one eye. At all following time points, the IP will be self-administered. Subjects will administer a single drop of IP into one eye two times throughout each dosing day separated by at least 8 hours.

Since only one randomly assigned eye will be treated, subjects will be handed out a bottle of topical lubricants (Genteal HA, Laboratoires Thea, France) as standard of care treatment for the control eye as needed. Subjects will be instructed to document instillation dates and times for Genteal HA eye drops in the diary.

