7. ADVERSE EVENTS

An AE is any untoward medical occurrence in a patient or clinical investigation subject administered a pharmaceutical product that does not necessarily have a causal relationship with this treatment. An AE can therefore be any unfavourable and unintended sign (including an abnormal laboratory finding), symptom, or disease temporally associated with the use of an IP, whether or not related to the IP.

Any pre-existing conditions or signs and/or symptoms present in a subject before the start of the study (i.e., before informed consent) should be recorded as medical/surgical history. Any medical occurrences that are new or worsened from the time of informed consent and up to and including the final visit must be reported as AEs or SAEs. All AEs and SAEs must be recorded irrespective of whether they are considered drug-related.

Subjects will be monitored throughout the study for adverse reactions to the study medications and/or procedures at each study visit. Questions will be posed in a non-leading manner so as not to bias the response. In addition to questioning at specific time points, subjects will be encouraged to report any AEs spontaneously. Subjects will also record any AEs occurring during the outpatient phase in a subject diary card. Any subject with an AE, SAE or clinically significant abnormal laboratory test value will be evaluated by the Investigator, or a monitoring physician, and will be treated and/or followed up until the symptoms or values have resolved or are assessed as stable by the Investigator. A physician, either at the Investigative site or at a nearby hospital emergency room, will administer treatment for any SAEs. Where appropriate, medical tests and examinations may be performed to ensure that an AE has fully resolved.

Adverse events and SAEs will be monitored throughout the study from the time a subject provides consent through to the final follow-up visit. Whenever possible, a specific disease or syndrome rather than individual associated signs and symptoms should be identified by the Investigator and

recorded on the subject's eCRF. However, if an observed or reported sign or symptom is not considered a component of a specific disease or syndrome by the Investigator, it should be recorded as a separate AE on the subject's eCRF.

Each AE or SAE reported will be assessed for severity and the date and time of onset (if available), relationship to dosing, duration and outcome of each event will be noted.

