9.6 Safety Analysis

Safety will be evaluated in the Safety Analysis Set by presenting summaries of AEs and vital signs.

Summary tables will be provided for all treatment-emergent AEs (TEAEs). A TEAE is defined as an AE with a start date and time on or after the first dose of study drug. Adverse events will be coded using the Medical Dictionary for Regulatory Activities (MedDRA®). The number and percentage of subjects with TEAEs will be tabulated by system organ class and MedDRA Preferred Term for each treatment group and by severity and relationship to treatment.

Adverse events leading to premature discontinuation from the study drug and serious TEAEs will be presented either in a table or a listing.

Descriptive statistics of vital signs and the change from baseline for each scheduled evaluation will be summarised at each study visit and the worst overall post-baseline value will be provided. The number and percent of subjects with treatment-emergent values with potential clinical significance will be tabulated.

Descriptive statistics of laboratory parameters and the change from baseline for each scheduled evaluation will be summarised at each study visit. The number and percent of subjects with treatment-emergent values of potential clinical significance will be tabulated by parameter.

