1.2 Study Design

In this prospective, single-centre, double-blind, placebo-controlled, randomised, parallel-group study will be conducted in accordance with the European Union Clinical Trial Directive 2001/20/EC and 2005/28/EC, the Declaration of Helsinki (revised version of Fortaleza, Brazil 2013), Good Manufacturing Practice, Good Clinical Practice and the current national regulations and guidelines. It will be approved by both the local ethics committee and regulatory authority prior to the first subject being screened.

A total of 24 healthy subjects aged between 18 and 64 years will be included into the first three cohorts of eight subjects each. Each cohort will be performed in two parts. In the first part, subjects will be randomised to receive a single dose of PP-001 or placebo. If safety and tolerability is acceptable, subjects will move on to Part II, where subjects will receive PP-001 or placebo according to the randomization in Part I four times a day for 12 consecutive days. If safety and tolerability is demonstrated in Part II, dose escalation will occur in the next cohort.

- In Cohort 1 six subjects will receive four drops of 0.05% (w/v) PP-001 in only one eye and two subjects will receive placebo in only one eye
- In Cohort 2 six subjects will receive four drops of 0.15% (w/v) PP-001 in only one eye and two subjects will receive placebo in only one eye
- In Cohort 3 six subjects will receive four drops of 0.30% (w/v) PP-001 in only one eye and two subjects will receive placebo in only one eye

Cohorts 1 to 3 will be performed in dose ascending order. On the first two study days in Part I of each cohort, one subject will be dosed per day. On the third study day up to two subjects can be dosed per day. On the following study

day(s) up to 4 subjects can be dosed per day. Randomization will be performed in two blocks (3:1, PP-001 vs. placebo) for each cohort. Part II will start at least 7 days after the last subject has been dosed in Part I and the Principal Investigator and the sponsor decide whether or not to continue dosing the cohort in Part II. Within each cohort neither subject nor investigator knows if the subject receives placebo or PP-001. A data safety monitoring board will decide if the safety and tolerability demonstrated in Parts I and II of the previous cohort warrant continuing the study at the next highest dose.

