In Cohort 4, twenty-one (21) subjects aged between 18 and 64 years with diagnosed ocular surface inflammation will be included. Subjects will receive half of the highest dose that was considered safe by the DSMB based on the safety data of cohorts 1-3. This cohort will be performed in one part (multiple instillations). Subject will receive two daily instillations for 12 consecutive days (in total 24 administrations). Out of 21 subjects, 14 subjects will receive PP-001 eye drops and 7 subjects will receive placebo. A data safety monitoring board will be installed for safety monitoring of cohort 4.

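### The Fisher tests of Cohorts 1, 2 and 3 against Cohort 4 compare raw adverse-event incidence over unequal planned windows (28 and 20 days after first dose) that the SAP does not align; for Cohort 3 the direction of the effect is unknown

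*SAP*

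**What the plan says.** SAP 2.5 states that "a Fisher's exact test will be calculated to compare the following treatment groups in the summary table for adverse events". Three of the five listed pairs set PP-001 recipients of Cohort 1, 2 or 3 against those of Cohort 4, the last being "Cohort 3 PP-001 vs. Cohort 4 PP-001". The same section adds a caveat: "The study is not powered for p-values and the p-values are just calculated for exploratory reason". The tests are reported in Table 4.1 (SAP 7.1).

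On the counting period, Protocol 7 says "Adverse events and SAEs will be monitored throughout the study from the time a subject provides consent through to the final follow-up visit". Protocol 9.6 gives treatment-emergent events a start but no end: "A TEAE is defined as an AE with a start date and time on or after the first dose of study drug". SAP 6.1 and Table 4.1 refer only to adverse events. They do not restrict to treatment-emergent events, set a time window or adjust for observation time.

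The final visit is Day 28 (±1) in Protocol Table 1 (Cohorts 1-3) and Day 20 (±1) in Protocol Table 2 (Cohort 4). SAP 2.4 recognises that the visit schedules differ, but only as a reason to split tables by time point.

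Planned numbers are in SAP 1.2: "In Cohort 3 six subjects will receive four drops of 0.30% (w/v) PP-001 in only one eye" (likewise six in Cohorts 1 and 2), and "Out of 21 subjects, 14 subjects will receive PP-001 eye drops and 7 subjects will receive placebo". SAP 2.11 records that the study was put on hold during Cohort 3 and that this cohort ended early.

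**The concern.** The proportion of subjects with at least one event grows with time at risk. If one group is watched for 28 days and the other for 20, the raw proportions differ even when the daily rate is the same. Protocol 9.1 names the between-cohort comparison as the treatment comparison of interest, and SAP 2.5 presents these tests as serving it.

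Healthy subjects and patients, and four drops and two drops a day, differ by design, and no analysis of these data can undo that. The window is different: it is a counting rule, and recorded onset dates allow it to be changed. Left as it is, it adds an avoidable component to the Cohort 1 and 2 contrasts and one of unknown sign to the Cohort 3 contrast, and a reader of Table 4.1 would see neither. The two PP-001 versus placebo tests in SAP 2.5 are made within one visit schedule and do not have this problem.

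**Working it through.** **Stated durations.** Protocol 3 gives 30 to 42 days from screening to last follow-up for Cohorts 1-3, and 22 to 35 days for Cohort 4. With screening on Day -14 to Day -2:
- Cohorts 1-3: 28 + 2 = 30 and 28 + 14 = 42.
- Cohort 4: 20 + 2 = 22, and 20 + 14 = 34, or 35 with the one-day visit window.

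The figures reproduce, so Day 28 and Day 20 are the intended ends.

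**Nominal window after first dose.** 28/20 = 1.40. Twenty-eight days is not fixed. Part II starts at least 7 days after the cohort's last Part I subject, and Part I doses one, one, up to two, then up to four subjects per day. If those are consecutive days and the cohort starts Part II together, the first subject is dosed 3 days before the last. Part II then begins for that subject on Day 10 or 11 (gap of 7 or 8 days), and the final visit falls on Day 30 or 31.

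**Effect on incidence at an equal constant hazard.** p28 = 1 - (1 - p20)^(28/20). The 20-day rate p20 is not in the documents, so it is varied. The last two columns give the chance of p ≤ 0.05 with the higher rate in the healthy group, by exact enumeration for 6 versus 14 subjects. The two-sided test and the 0.05 level are assumptions; the SAP states neither.

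| p20 | p28 | Excess (points) | Equal windows | 28 vs 20 days |
|---|---|---|---|---|
| 10% | 13.7% | 3.7 | 0.4% | 1.1% |
| 20% | 26.8% | 6.8 | 1.2% | 3.1% |
| 30% | 39.3% | 9.3 | 1.8% | 4.6% |
| 40% | 51.1% | 11.1 | 1.9% | 5.1% |
| 50% | 62.1% | 12.1 | 1.6% | 4.4% |

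The excess peaks at 12.3 points, near p20 = 57%. Total rejection in both directions is at most about 5.5% for p20 from 10% to 80%.

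**Other assumptions, at a 30% rate in Cohort 4.**
- Events only on dosing days: 13 days (Day 0 and Days 8-19) against 12 (Days 0-11). 1 - 0.7^(13/12) = 32.0%, an excess of 2.0 points.
- Events counted from consent, 14-day screening in both: 42/34 = 1.24. 1 - 0.7^(42/34) = 35.6%.
- Events counted from consent, 2-day screening in both: 30/22 = 1.36, giving 38.5%.
- A subject followed to Day 31: 31/20 = 1.55, giving 42.5%.

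**Cohort 3.** Actual follow-up is not given. If it averaged 12 days (illustrative) and the 20-day rate were 40%, incidence would be 1 - 0.6^(12/20) = 26.4% against 40.0%. Below 20 days the effect reverses; above 20 days it keeps the planned sign.

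**Net direction.** A patient hazard above 1.40 times the healthy hazard outweighs the window. With a doubled patient hazard and a healthy 20-day rate of 30%, incidence is 39.3% in healthy subjects and 1 - 0.7^2 = 51.0% in patients. The excess still shows, reduced from 21.0 to 11.7 points.

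**Aligned window.** From the first repeat dose to follow-up: 28 - 8 = 20 days and 20 - 0 = 20 days. Dosing days are 12 and 12. Days after the last dose are 28 - 19 = 9 and 20 - 11 = 9. At an equal hazard the window difference is then zero, and total rejection is 0.4% to 3.2% for p20 from 10% to 80%.

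**The case against.** A reader might infer that all three tests are biased the same way, or that the plan makes patients look safer. The documents support neither. Cohort 3 was stopped early with unknown follow-up. The cohorts also differ in population, in drops per day (4 against 2), in total doses (49 against 24) and, for Cohorts 1 and 3, in concentration. The window is one component of a confounded contrast, and its sign is not the sign of the whole.

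The size also depends on the assumptions. The extra eight days are one single-drop day and an undosed week, so the constant-hazard figure may be well above the true one. Nor is the effect on the p-values dramatic: total rejection stays near or below 5%, no decision rule uses these tests, and the SAP calls them exploratory. The Cohort 4 PP-001 versus Cohort 4 placebo test is randomised, has equal windows, and is the better evidence on drug-related excess in patients. All of this stands.

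The exploratory label, however, concerns power. It does not address unequal time at risk in a comparison the protocol names as being of interest.

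Starting the count at Part II has its own cost. Subjects enter Part II only if Part I was acceptable, so first-exposure reactions leave the healthy side and remain in Cohort 4. Examination intensity still differs: on Days 8 and 9 all four doses are given on site with a slit-lamp examination after each, whereas in Cohort 4 only the first instillation on Days 0 and 1 is given on site. This is why the aligned contrast should sit beside the all-events one and should not be called an exact match.

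**Conclusion.** The point holds in limited form. By plan, these three tests compare raw incidence over 28 and 20 nominal days after first dose, somewhat longer for subjects dosed early in Part I, and the SAP does nothing to align them. At an equal daily rate this raises incidence in Cohorts 1 and 2 by about 4 to 12 points for 20-day rates of 10% to 50% under a constant hazard. The excess is as little as 2 points at a 30% rate if events arise only on dosing days, and intermediate if events from consent are counted. The event rate, hazard shape, two-sided 0.05 level and planned group sizes are assumptions of the calculation. For Cohort 3 the direction is unknown, and the net direction of any of the three comparisons cannot be stated. The consequence is modest, but it is avoidable at little cost and should be dealt with in the SAP before unblinding.

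**What to change.** Add to SAP 2.5, for the three contrasts against Cohort 4 only:
- Count events with onset from the first repeat-dose administration (first Part II dose in Cohorts 1-3, Day 0 dose in Cohort 4) to the follow-up visit.
- Use as denominator the subjects who received at least one dose in that period.
- Report actual observation days per column, including Cohort 3. Alignment fixes the start of the window; if follow-up in Cohort 3 was cut short, only the reported days let a reader judge what remains.
- Keep the all-events counts and tests in Table 4.1 beside the aligned ones, and state whether all-events means from consent or from first dose.

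The cost is a short addition to the SAP and an onset-date filter on data already recorded. The downside should be written into the SAP: Part I first-exposure events, and subjects who never entered Part II, drop out of the aligned contrast, while differences in examination intensity, drops per day and population remain.

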1. OVERVIEW

1.1 Study Objectives

1.1.1 Primary Objective

The primary objective is to assess the safety and tolerability of 1 day (single dose) and 12 days (48 doses) dosing with ascending doses (0.05% [0.5 mg/mL], 0.15% [1.5 mg/mL] and 0.3% [3.0 mg/mL]) of PP-001 eye drops compared to placebo eye drops in healthy subjects (cohorts 1-3). In addition, safety and tolerability will be tested in a group of 21 patients with ocular surface inflammation (cohort 4).

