2.3 Blinding and Randomization

This is a double-blind study within each cohort. Subjects will receive either PP-001 or placebo. Randomization will be done in two blocks of 4 subjects per block (3:1, PP-001 vs. placebo) for each of the three cohorts (cohorts 1-3).

For cohort 4, randomization will be performed in a 2:1 ratio (14 subjects will receive the PP-001 and 7 will receive placebo). Subjects within one cohort will not be aware whether they are receiving PP-001 or placebo. The investigators will not know whether a subject receives PP-001 or placebo within a cohort. The IP will be provided in pre-packaged eye drop bottles which will be labelled in a double-blind fashion.

General unblinding of ADMB personnel and the sponsor will occur after database closure, for final statistical analysis.

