2.4 Descriptive Analyses and Columns in Summary Tables

Descriptive analyses of continuous variables (summary statistics) will be described with the number of non-missing observations, arithmetic mean, standard deviation (\pm SD), median, quartiles (Q1 and Q3) and range (minimum and maximum).

Categorical variables (frequency statistics) will be described with the number of non-missing observations and percentages (%). Percentages will be calculated within each stratum on the total number of non-missing observations, if not stated otherwise.

In general, tables will present the following columns:

- Cohort 1 PP-001, 0.05% [0.5 mg/mL], 4 drops per day, healthy subjects
- Cohort 2 PP-001, 0.15% [1.5 mg/mL], 4 drops per day, healthy subjects
- Cohort 3 PP-001, 0.3% [3.0 mg/mL], 4 drops per day, healthy subjects
- Cohort 1-3 PP-001 pooled
- Cohort 4 PP-001, 0.15% [1.5 mg/mL], 2 drops per day, patients with diagnosed ocular surface inflammation
- Placebo subjects from all cohort 1-3
- Placebo subjects from cohort 4
- All subjects (only for overall study information and baseline tables)

The disposition table may also include a column for screening failures. For tables by time point the columns for Cohort 1-3 and Cohort 4 might be shown in a separate table, since Cohort 1-3 have a different visit schedule than Cohort 4.

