2.11 Changes in the Conduct of the Study or Planned Analysis

In CSP Version 4.0 (March 26, 2021), which is the latest protocol version at the time when writing this SAP, concomitant medication is mentioned erroneously as primary endpoint. This is not included as a primary endpoint in the SAP, since it is not considered a relevant safety endpoint.

The recruitment of the first healthy subject in Cohort 1-3 was in November 2018. In June 2019, the study was placed on-hold while Cohort 3 was in progress, and Cohort 3 was stopped prematurely. The study was re-started with addition of a 4th Cohort which recruits patients with ocular surface inflammation starting in May 2021.

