7.1 List of Tables

No.	Legend	Comment
Overall study information		
1.1.1	Subject overview (all subjects)	
1.1.2	Protocol deviations (safety analysis set)	
1.1.3	Attended visits with dates (safety analysis set)	
1.1.4	Study completion (safety analysis set)	
1.1.5	Study drug administration (safety analysis set)	
1.2.2 -	Repeat tables for ITT analysis set, if not the same as safety analysis set.	
1.2.5		
Baseline evaluation		
2.1.1	Summary table of demographic information (safety analysis set)	
2.1.2	Summary table for medical and ophthalmic histories and prior and concomitant medication (safety analysis set)	
2.1.3	Non-pharmacologic treatments and procedures (safety analysis set)	
2.2.1 -	Repeat tables for ITT analysis set, if not the same as safety analysis set.	
2.2.3		
Pharmacodynamics Analysis		
3.1.1	Pharmacodynamics by time point (ITT analysis set)	
3.2.1	Repeat table for PP analysis set.	
Safety Analysis		
4.1	Summary table for adverse events (safety analysis set)	Including tests described in section 2.5.
4.2	Adverse events by SOC and PT (safety analysis set)	
4.3	Adverse events by severity (safety analysis set)	
4.4	Adverse events by maximum severity (safety analysis set)	"By maximum severity" is explained in section 6.1.
4.5	Adverse events by causality (safety analysis set)	
4.6	Adverse events by maximum causality (safety analysis set)	"By maximum causality" is explained in section 6.1.
4.7	Laboratory results by time point (safety analysis set)	

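### SAP 2.5 tests no single healthy dose against placebo or another healthy dose and has no dose-trend test; one exploratory exact trend test would fit the ascending-dose objective

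*SAP*

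**What the plan says.** The primary objective (SAP 1.1.1) concerns "ascending doses (0.05% [0.5 mg/mL], 0.15% [1.5 mg/mL] and 0.3% [3.0 mg/mL]) of PP-001 eye drops compared to placebo eye drops in healthy subjects". Cohort 4 is added as a separate group of patients; for that group the objective does not name a placebo comparison.

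SAP 2.5 lists five Fisher tests:

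- Cohort 1, Cohort 2 and Cohort 3 PP-001, each against Cohort 4 PP-001. The last is "Cohort 3 PP-001 vs. Cohort 4 PP-001".
- "Cohort 1-3 PP-001 pooled vs. Placebo subjects from all Cohort 1-3".
- Cohort 4 PP-001 against Cohort 4 placebo.

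The results go into Table 4.1, which SAP 7.1 annotates "Including tests described in section 2.5". SAP 2.5 adds that the study is not powered for p-values and that "the p-values are just calculated for exploratory reason".

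Randomisation is within cohort. For the healthy cohorts, SAP 2.3 states: "Randomization will be done in two blocks of 4 subjects per block (3:1, PP-001 vs. placebo) for each of the three cohorts". The Cohort 4 column is defined in SAP 2.4 as "Cohort 4 PP-001, 0.15% [1.5 mg/mL], 2 drops per day, patients with diagnosed ocular surface inflammation", while the healthy columns are at four drops per day. SAP 2.11 records: "In June 2019, the study was placed on-hold while Cohort 3 was in progress, and Cohort 3 was stopped prematurely". The number of subjects dosed in that cohort is not given.

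**The concern.** The design escalates through three concentrations, so the natural question is whether AEs become more frequent with dose, relative to placebo, in healthy subjects. Among the five tests, the one that uses healthy placebo averages dose away. The three that keep the healthy doses apart all use patients on another regimen as comparator. A steep excess at the top dose could therefore appear in Table 4.1 beside an unremarkable pooled p-value, and the only other test of that cohort would be one in which dose cannot be separated from disease and schedule.

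**Working it through.** **Inputs.** Planned numbers (SAP 1.2, 1.4, 2.3): 3 × 6 = 18 healthy subjects on PP-001, 3 × 2 = 6 on healthy placebo, and 14 on PP-001 plus 7 on placebo in Cohort 4. The documents give no AE rates, significance level or sidedness. I assume two-sided 0.05 and a range of rates, and count subjects with at least one AE. The SAP states no power figure to reproduce. All results come from exact enumeration.

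**1. What the five tests cover.** Healthy dose vs healthy placebo: none. Healthy dose vs another healthy dose: none. Trend: none. Pooled healthy doses vs healthy placebo: one. Within Cohort 4: one. Healthy cohort vs patients: three.

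**2. What the pooled test needs, with 0/6 on placebo.**

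- 9/18 on PP-001: C(18,9)/C(24,9) = 48620/1307504 = 0.0372. Adding the equally or less likely tables gives p = 0.052.
- 10/18: C(18,10)/C(24,10) = 43758/1961256 = 0.0223. With the opposite tail, p = 0.024.

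Ten events are needed, and one dose group holds six subjects. An effect confined to one dose therefore cannot reach 0.05 when the other healthy groups have no events.

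**3. Example: 6/6 at 0.30%, none in the other healthy groups.**

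- Pooled test: C(18,6)/C(24,6) = 18564/134596 = 0.138; two-sided p = 0.277.
- Exact trend, scores 0-1-2-3: only the two extreme allocations are as far from expectation, so p = 2/134596 = 0.000015.
- Planned Cohort 3 vs Cohort 4, if 0/14 patients have an AE: p = 1/C(20,6) = 1/38760 = 0.00003. With 5, 4 or 3 of 6 it is 0.0004, 0.003 and 0.018.

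**4. Power at assumed AE rates, six subjects per group.**

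| Placebo / 0.05 / 0.15 / 0.30% | Pooled | Trend (0-3) |
|---|---|---|
| 10/10/10/80 | 0.5% | 74% |
| 10/20/40/70 | 10% | 61% |
| 10/20/30/40 | 1% | 16% |
| 10/30/30/30 | 1% | 5.5% |
| 10/80/80/80 | 83% | 66% |
| 10/70/70/40 | 43% | 9% |

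The trend test gains much when the effect is steep, little when it is modest, and loses when the effect plateaus or falls at the top dose. At a flat 20% the chance that either test gives p<0.05 is 3.2%.

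**5. Planned Cohort 3 vs Cohort 4 test (6 vs 14), 80% at 0.30%.** Power is 87.7%, 71.5% and 50.7% if 10%, 20% and 30% of patients have an AE. The groups are not randomised against each other and differ in:

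- disease;
- concentration, 0.30% vs 0.15%;
- drops per day, 4 vs 2;
- number of doses, 1 + 48 = 49 vs 24 (Protocol 5.2);
- last visit, Day 28 vs Day 20 (Protocol Tables 1 and 2);
- calendar period, recruitment from November 2018 vs May 2021 (SAP 2.11).

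**6. False positives across the three healthy-vs-patient tests, no drug effect, 20% AEs in healthy subjects.** At least one gives p<0.05 in 3.6% of trials if patients also have 20%, and in 3.1%, 10% and 27% if patients have 30%, 40% and 50%. An excess arises only if patient AE rates are clearly higher. Protocol 7 counts only new or worsened events, so pre-existing disease does not by itself make them so.

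**7. Shortfall in Cohort 3.** With an assumed 2, 3, 4 or 5 top-dose subjects, trend power at 10/20/40/70 falls from 61% to 35%, 45%, 56% or 59%.

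**The case against.** A reader might infer that the plan contains no test by dose, so that a top-dose signal would meet only the pooled test. The documents do not support that. Cohort 3 against Cohort 4 is a planned test in Table 4.1 and is sensitive to such a signal when patient AE rates are low (steps 3 and 5). What stands is narrower: that test has no placebo and mixes dose with population and schedule.

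A reader might also infer that the three healthy-versus-patient tests are errors to be removed. Protocol 9.1 names a comparison between cohorts as the comparison of interest, and SAP 2.5 carries it out. The protocol does not require these particular tests, but they are consistent with it. The false-positive excess rests on assumed higher patient rates. Dropping the p-values is a preference and would give up the sensitivity just described.

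The exploratory status is a fair defence. No sample size rests on these p-values, and escalation belongs to the DSMB. Doses have separate columns, AEs are tabulated by SOC and preferred term, severity and causality, and every subject's events are listed. This limits the weight of the point but does not explain why the tests that are printed leave out dose against placebo.

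The trend test has weaknesses too. It compares sequential cohorts not randomised against each other, and it leans on a cohort that stopped early. It does stay within one population and one planned schedule.

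**Conclusion.** The point holds as a mismatch between the planned contrasts and the ascending-dose objective, and as a cheap improvement. It is not a failed analysis. No planned test compares a healthy dose with healthy placebo or with another healthy dose, and the pooled test is nearly blind to an effect confined to one dose: 0.5% power against 74% for a trend test at 10/10/10/80, and 10% against 61% at 10/20/40/70. For modest effects neither helps much (trend 5.5% to 16%). All power figures rest on assumed AE rates, a two-sided 0.05 level and the planned numbers, which Cohort 3 may not have reached. The p-values remain exploratory and no decision depends on them.

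**What to change.** In SAP 2.5:

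1. Keep the planned tests. The pooled test must stay because it does better for a plateau (83% vs 66%) and if truncated exposure lowers top-dose AEs (43% vs 9%).
2. Add one exploratory exact Cochran-Armitage trend test on subjects with at least one AE, across pooled healthy placebo, 0.05%, 0.15% and 0.30%. Fix the scores before unblinding. Scores 0-3 are reasonable. Concentration scores 0/0.5/1.5/3 do better for a top-dose-only effect (85% vs 74%) and worse for a plateau (46% vs 66%). With the pooled test kept, the chance that either test gives p<0.05 under the plateau is 87% or 86%, so either set is defensible.
3. Footnote the trend result with the number of Cohort 3 subjects dosed.
4. Label the three healthy-versus-Cohort 4 contrasts in Table 4.1 as non-randomised. Dropping their p-values is optional.

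The cost is SAP wording and a few lines of code, with no new data. The number of exploratory p-value contrasts rises from five to six.
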